- NO/GTN lowers BP in acute/subacute stroke and so may 'move' patients down the epidemiological curve relating high BP and poor outcome. This mechanism may be of particular relevance in ICH.
- NO dilates cerebral arteries (e.g. middle cerebral) so could increase 'front door' cerebral blood flow (CBF) and peri-lesional perfusion, as seen in the GTN-3 pilot trial.
- NO dilates pial arteries (shown experimentally) so might increase CBF via the 'back-door'.
- NO donors are neuroprotective in preclinical stroke, especially if given early.
- Endogenous NO levels are low in acute stroke; hence, administration will supplement low [NO].
- GTN may 'prime' patients for rt-PA by lowering their BP so that more can be treated, and more rapidly after hospital arrival. RIGHT showed non-significant trends for these.
- GTN, through cerebral vasodilation, may increase access of alteplase to obstructing clot and therefore increase the effectiveness of thrombolysis, i.e., GTN might be additive to rt-PA.

Several NO donors are licensed in the UK and are used widely in patients with ischaemic heart disease, heart failure and severe hypertension; these include intravenous sodium nitroprusside and transdermal glyceryl trinitrate. One uncontrolled pilot study found that sodium nitroprusside lowered BP without altering cerebral perfusion (assessed using CT SPECT), and attenuated platelet function, in patients with recent ischaemic stroke. Four

phase II and two phase III randomised controlled trials have assessed transdermal glyceryl trinitrate in patients with acute stroke (IS and ICH) (Table 1).

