## **RANDOMISATION AND BLINDING**

All participants eligible for inclusion will be randomised centrally using a secure internet site in real-time. Randomisation will be 1:1 GTN: sham and involve computerised stratification by stroke type (ischaemic stroke or not known vs ICH) and minimisation on age, severity, time, systolic blood pressure and candidate for or received reperfusion therapy (alteplase, and/or mechanical thrombectomy). This approach ensures concealment of allocation, minimises differences in key baseline prognostic variables, and slightly improves statistical power (16). Patients, relatives, researchers, and outcome assessors will be masked to treatment allocation.

In order to minimise selection bias, a participant must be enrolled in the study before they are randomised on the internet site. Randomisation will allocate a number corresponding to a treatment pack and the participant will receive treatment from the allocated numbered pack.

In the event of computer failure (for example: server failure), investigators will follow the working practice document for computer system disaster recovery, which will allow the participant to be randomised following standardised operating procedure.

Personnel applying the GTN/sham patches will not be blinded to the treatment allocation as the sachets around the patches are different and carry the manufacturers identifying information.

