### **11 Randomisation**

Patients will be randomised 1:1 to receive either 5 mg transdermal GTN versus sham transdermal DuoDERM hydrocolloid dressing placed on the back or shoulders for two days. Randomisation will be performed by the Stroke Trials Unit (STU) in Nottingham and involve computerised stratification by stroke type (IS or not known; ICH) and minimisation on age, severity, time, systolic blood pressure and candidate for or received reperfusion therapy. Patients, relatives, researchers, and outcome assessors will be masked to treatment allocation.

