#### ***24b Secondary endpoints***

1. Hospital admission:
  - Neurological impairment (NIHSS)
  - Systolic and diastolic blood pressure, heart rate.
  - Proportion of participants with systolic blood pressure <185 mmHg.
  - Feeding and dysphagia (dysphagia severity rating scale)
  - Stroke lesion size on brain scan (non-contrast CT or T2 MR).
  - Amount of cerebral arterial patency on brain scan (CT or MR angiography).
2. Hospital utilisation:
  - Open-label blood pressure lowering.
  - Intravenous thrombolysis.
  - Mechanical thrombectomy.
  - Hyperacute stroke unit.
  - Stroke Rehabilitation Unit.
  - Physiotherapy.
  - Occupational therapy.
  - Speech & language therapy.
  - Surgery for IS - Hemicraniectomy.
  - Surgery for ICH.
  - Days in intensive/critical care unit.
3. At day 2:
  - Systolic and diastolic blood pressure, heart rate.

4. At day 2: Biomarkers
  - Blood biomarkers (exact measures to be determined by literature review prior to measurement but examples include S-100, NOx).
  - Genetic markers (exact measures to be determined by literature review prior to measurement but examples include NO synthase polymorphisms).
5. At day 2 (or discharge if sooner):
  - Neurological impairment (NIHSS).
  - Stroke recurrence.
  - Neurological deterioration from baseline (NIHSS  $\geq 4$  points, or  $\geq 2$ -point increase in any domain).
  - Feeding and dysphagia (DSRS).
6. At discharge/death
  - Length of stay in hospital.
  - Patient disposition.
7. At day 90 by telephone (or post):
  - Dependency – modified Rankin Scale (primary clinical endpoint at Day 90).
  - Disability/activities of daily living - Barthel Index (BI).
  - Quality of life - health utility status (HUS, derived from EuroQoL-5D), EQ-Visual Analogue Scale (EQ-VAS).
  - Cognition - telephone-MMSE, telephone interview cognition scale (TICS), animal naming.
  - Mood - Zung depression scale.
  - Patient disposition (died, institution/in hospital, home).

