### **25c Analyses of secondary outcomes**

Mechanistic, clinical and safety outcomes will be compared between the treatment groups using binary logistic regression, Cox proportional hazards regression (death), ordinal logistic regression (mRS) or multiple linear regression (BI, TICS, t-MMSE, ZDS, EQ-5D, EQ-VAS, as appropriate (**Table A**), in exploratory analyses.

**25d Covariate adjustment:** Analyses will be adjusted for minimisation covariates including age, stroke severity (NIHSS), time after stroke, systolic blood pressure, and received reperfusion therapy.

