### **26 Subgroup analyses:**

The primary clinical outcome will be analysed in subgroups consisting of the minimisation factors:

- Age (years):  $\leq 70$ ,  $> 70$
- Stroke severity, NIHSS (/42):  $\leq 10$ ,  $> 10$
- Time after stroke (minutes):  $\leq 220$ ,  $> 220$
- Systolic blood pressure (mmHg):  $\leq 160$ ,  $> 160$
- Received reperfusion therapy: yes, no

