**Main paper tables****Table 1. Baseline characteristics by treatment group transdermal glyceryl trinitrate (GTN).**

Data are number (%), median [interquartile range] or mean (standard deviation).

† Minimisation variables include age, severity, time, systolic blood pressure, and candidate for or received reperfusion therapy.

Characteristic	Statistic	N	All	GTN	Control
Patients randomised	N		xxx	xxx	xxx
Age (years) †	Mean (SD) (range)	xxx	xxx (xxx) (xxx)	xxx (xxx) (xxx)	xxx (xxx) (xxx)
Sex (males)	n (%)	xxx	xxx (xxx)	xxx (xxx)	xxx (xxx)
Onset to randomisation (minutes) †	Median [IQR] (range)	xxx	xxx [xxx] (xxx)	xxx [xxx] (xxx)	xxx [xxx] (xxx)
Weight	Mean (SD) (range)	xxx	xxx (xxx) (xxx)	xxx (xxx) (xxx)	xxx (xxx) (xxx)
Ethnicity					
...White	n (%)	xxx	xxx (xxx)	xxx (xxx)	xxx (xxx)
...Black	n (%)	xxx	xxx (xxx)	xxx (xxx)	xxx (xxx)
...Asian	n (%)	xxx	xxx (xxx)	xxx (xxx)	xxx (xxx)
...Other	n (%)	xxx	xxx (xxx)	xxx (xxx)	xxx (xxx)
Wake-up stroke	n (%)	xxx	xxx (xxx)	xxx (xxx)	xxx (xxx)
From Nursing home	n (%)	xxx	xxx (xxx)	xxx (xxx)	xxx (xxx)
Medical history					
Diabetes mellitus	n (%)	xxx	xxx (xxx)	xxx (xxx)	xxx (xxx)
Atrial fibrillation	n (%)	xxx	xxx (xxx)	xxx (xxx)	xxx (xxx)
Previous stroke	n (%)	xxx	xxx (xxx)	xxx (xxx)	xxx (xxx)
Previous TIA	n (%)	xxx	xxx (xxx)	xxx (xxx)	xxx (xxx)
IHD	n (%)	xxx	xxx (xxx)	xxx (xxx)	xxx (xxx)
Hyperlipidaemia	n (%)	xxx	xxx (xxx)	xxx (xxx)	xxx (xxx)
PAD	n (%)	xxx	xxx (xxx)	xxx (xxx)	xxx (xxx)
Family stroke	n (%)	xxx	xxx (xxx)	xxx (xxx)	xxx (xxx)
Smoking (%)					
...Current	n (%)	xxx	xxx (xxx)	xxx (xxx)	xxx (xxx)

Characteristic	Statistic	N	All	GTN	Control
...Past	n (%)	xxx	xxx (xxx)	xxx (xxx)	xxx (xxx)
...Never	n (%)	xxx	xxx (xxx)	xxx (xxx)	xxx (xxx)
Alcohol intake (%)					
...High (over 21 units per week)	n (%)	xxx	xxx (xxx)	xxx (xxx)	xxx (xxx)
...Moderate (1-21 units per week)	n (%)	xxx	xxx (xxx)	xxx (xxx)	xxx (xxx)
...None	n (%)	xxx	xxx (xxx)	xxx (xxx)	xxx (xxx)
Existing medications prior to stroke n (%)					
Nitrate therapy	n (%)	xxx	xxx (xxx)	xxx (xxx)	xxx (xxx)
Lipid lowering	n (%)	xxx	xxx (xxx)	xxx (xxx)	xxx (xxx)
Antihypertensives					
Antihypertensives	n (%)	xxx	xxx (xxx)	xxx (xxx)	xxx (xxx)
Diuretic	n (%)	xxx	xxx (xxx)	xxx (xxx)	xxx (xxx)
Beta Blocker	n (%)	xxx	xxx (xxx)	xxx (xxx)	xxx (xxx)
Alpha-blocker	n (%)	xxx	xxx (xxx)	xxx (xxx)	xxx (xxx)
Calcium channel blocker	n (%)	xxx	xxx (xxx)	xxx (xxx)	xxx (xxx)

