**Table 3. Clinical Outcomes at Day 90.**

Data are number (%), median [interquartile range] or mean (standard deviation). Analyses performed using binary logistic regression (BLR), ordinal logistic regression (OLR) or multiple linear regression (MLR) with adjustment for age, time from stroke onset to randomisation, systolic blood pressure, stroke severity (NIHSS), and received reperfusion therapy. Mean (SD) and MLR will be used instead of median [IQR] and OLR for ordinal scales with more than 7 levels (central limit theorem/large sample). Cox proportional hazards regression (CPHR) will be used for death.

Variable	Statistic	N	All	GTN	Sham	aOR/aHR/aMD (95%CI)	Difference (p)
Patients randomised	N	xxx	xxx	xxx	xxx		
Outcomes							
Functional, modified Rankin scale (/6)							
	Median [IQR]	xxx	xxx [xxx]	xxx [xxx]	xxx [xxx]	xxx (xxx, xxx)	aOLR
	Mean (SD)	xxx	xxx [xxx]	xxx [xxx]	xxx [xxx]	xxx (xxx, xxx)	OLR aMLR
0	n(%)	xxx	xxx (xxx)	xxx (xxx)	xxx (xxx)		
1	n (%)	xxx	xxx (xxx)	xxx (xxx)	xxx (xxx)		
2	n (%)	xxx	xxx (xxx)	xxx (xxx)	xxx (xxx)		
3	n (%)	xxx	xxx (xxx)	xxx (xxx)	xxx (xxx)		
4	n (%)	xxx	xxx (xxx)	xxx (xxx)	xxx (xxx)		
5	n (%)	xxx	xxx (xxx)	xxx (xxx)	xxx (xxx)		
6	n (%)	xxx	xxx (xxx)	xxx (xxx)	xxx (xxx)		
Death	n (%)	xxx	xxx (xxx)	xxx (xxx)	xxx (xxx)	xxx (xxx, xxx)	CPHR
Disability							
Barthel index, BI (/100)	Mean (SD)	xxx	xxx (xxx)	xxx (xxx)	xxx (xxx)	xxx (xxx, xxx)	MLR
Cognition							
Telephone, MMSE (/22)	Mean (SD)	xxx	xxx (xxx)	xxx (xxx)	xxx (xxx)	xxx (xxx, xxx)	MLR
TICS-M (/39)	Mean (SD)	xxx	xxx (xxx)	xxx (xxx)	xxx (xxx)	xxx (xxx, xxx)	MLR
Animal naming	Mean (SD)	xxx	xxx (xxx)	xxx (xxx)	xxx (xxx)	xxx (xxx, xxx)	MLR
Mood							
Zung depression scale, ZDS(/102.5)	Mean (SD)	xxx	xxx (xxx)	xxx (xxx)	xxx (xxx)	xxx (xxx, xxx)	MLR

Variable	Statistic	N	All	GTN	Sham	aOR/aHR/aMD (95%CI)	Difference (p)
Quality of Life							
EQ-5D HSUV (/1)	Mean (SD)	xxx	xxx (xxx)	xxx (xxx)	xxx (xxx)	xxx (xxx, xxx)	OLR
EQ-VAS (/100)	Mean (SD)	xxx	xxx (xxx)	xxx (xxx)	xxx (xxx)	xxx (xxx, xxx)	OLR
Disposition						xxx (xxx, xxx)	OLR
...Home	n (%)	xxx	xxx (xxx)	xxx (xxx)	xxx (xxx)		
...Institution/in hospital	n (%)	xxx	xxx (xxx)	xxx (xxx)	xxx (xxx)		
...Died	n (%)	xxx	xxx (xxx)	xxx (xxx)	xxx (xxx)		
Events							
Recurrent Stroke	n (%)	xxx	xxx (xxx)	xxx (xxx)	xxx (xxx)	xxx (xxx, xxx)	BLR

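### Models and one subgroup use receipt of reperfusion therapy, with no time limit, instead of the minimisation factor (candidate for or received), which can bias the exploratory comparisons

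*SAP*

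**What the plan says.** **Randomisation.** SAP section 11 describes "minimisation on age, severity, time, systolic blood pressure and candidate for or received reperfusion therapy". The protocol (Synopsis; Randomisation and blinding) gives the same factor, and the legend of SAP Table 1 agrees: "Minimisation variables include age, severity, time, systolic blood pressure, and candidate for or received reperfusion therapy".

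**Analysis.** SAP 25d reads: "Analyses will be adjusted for minimisation covariates including age, stroke severity (NIHSS), time after stroke, systolic blood pressure, and received reperfusion therapy". The Table 3 footnote specifies Day 90 models "with adjustment for age, time from stroke onset to randomisation, systolic blood pressure, stroke severity (NIHSS), and received reperfusion therapy". Section 26, which says its subgroups are the minimisation factors, lists "Received reperfusion therapy: yes, no".

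**Receipt as an endpoint.** SAP 24b lists "Intravenous thrombolysis" and mechanical thrombectomy among the secondary endpoints, under hospital utilisation.

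**Receipt as something GTN might change.** The protocol background says that GTN may prime "patients for rt-PA by lowering their BP so that more can be treated", and adds that the earlier RIGHT trial showed only non-significant trends in this direction.

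**The concern.** The two variables differ. A participant who is a candidate at randomisation but is never treated counts as yes for minimisation and no for analysis. The SAP calls its covariate and subgroup minimisation factors, so read literally it departs from its own intent and leaves the true factor out.

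Receipt also has no time limit. If some of it is decided after randomisation and GTN alters it, adjusting for it removes any part of the GTN effect that runs through reperfusion. If unmeasured prognosis also influences who is treated, adjustment opens a non-causal path between arm and outcome. Splitting on receipt has the same weakness, because the two subgroups are then partly formed by treatment.

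At stake are the adjusted mRS estimate (the primary clinical outcome), the other adjusted comparisons and one of the five subgroups. These are the efficacy signals that the secondary objectives ask for.

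**Working it through.** **1. Can receipt follow randomisation?** Yes, for some participants.
- Protocol, Recruitment: where a patient lacks capacity and no relative is present, the patch may go on first so that CT and thrombolysis are not held up.
- Protocol, Inclusion criteria and Radiation exposure: the scan may come before or after trial treatment starts.
- The randomisation stratum combines ischaemic stroke with type not yet known, so unscanned patients are expected.
- SAP Table C, note 4: thrombolysis and thrombectomy are recorded under hospital utilisation, in the discharge/death column. A programmer could properly use receipt at any time in the stay.

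No document gives the share treated before randomisation.

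**2. Size.** The plan has no figure for this point to reproduce. Its statement of a detectable odds ratio of 0.51 with 100 participants is a separate matter; 0.51 is only borrowed below as an assumed direct effect.

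Every simulation input is an assumption: 60% are candidates; half of those not already treated go on to treatment under sham (0.60 × 0.50 = 30%); the odds ratio of reperfusion on worse mRS is 0.6. GTN multiplies the odds of later treatment by 1.0, 1.5 or 2.0. From even odds, 1.5 gives 0.60 × 1.5/2.5 = 36% and 2.0 gives 0.60 × 2/3 = 40%. In rows marked U, an unmeasured factor worsens mRS and lowers the chance of treatment (log-odds coefficients 0.8 and −0.8). There are 120,000 simulated patients per row, fitted by ordinal logistic regression with severity plus one of the two reperfusion terms.

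| Direct GTN OR; GTN effect on receipt (OR) | Received, sham / GTN | OR, candidate-adjusted | OR, received-adjusted | Ratio |
|---|---|---|---|---|
| 1.00; 1.0 | 30.4% / 29.7% | 0.988 | 0.984 | 1.00 |
| 1.00; 1.0, U | 29.7% / 30.0% | 1.014 | 1.016 | 1.00 |
| 1.00; 2.0, U, all treated before randomisation | 59.9% / 60.2% | 0.997 | 0.997 | 1.00 |
| 1.00; 2.0, U, half of candidates treated before | 45.3% / 49.3% | 0.993 | 1.020 | 1.03 |
| 1.00; 1.5 | 30.0% / 35.7% | 0.971 | 1.001 | 1.03 |
| 1.00; 2.0 | 30.3% / 39.8% | 0.962 | 1.013 | 1.05 |
| 1.00; 1.5, U | 30.0% / 35.6% | 0.992 | 1.038 | 1.05 |
| 1.00; 2.0, U | 29.7% / 38.7% | 0.943 | 1.013 | 1.07 |
| 0.51; 1.5, U | 29.8% / 35.5% | 0.544 | 0.561 | 1.03 |
| 0.51; 2.0, U | 30.4% / 38.9% | 0.545 | 0.577 | 1.06 |

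Ratio = received-adjusted OR ÷ candidate-adjusted OR, for example 1.013/0.943 = 1.07. Single odds ratios carry about 1% simulation error (√(12/(120,000 × 0.98)) = 0.010). The two in a row come from the same patients, so the ratio is steadier.

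The subgroups move too. In the row 1.00; 2.0, U, the odds ratio is 1.043 among those treated and 0.998 among those not, against 0.943 overall.

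**3. Stronger assumptions.** Take receipt rising from 33% to 51%, a reperfusion odds ratio of 0.50, and log-odds coefficients on mRS of 1.2 for severity and 0.8 for the unmeasured factor.
- Worse unmeasured prognosis lowers receipt: 0.90 becomes 1.12 (ratio 1.24). If reperfusion has no effect, 1.00 becomes 1.12.
- Worse prognosis raises receipt: 0.88 stays 0.88. If reperfusion has no effect, 0.99 becomes 0.89.

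So the direction is not fixed either.

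**4. Against the trial's precision.** With seven roughly equal mRS levels (assumed) and 120 participants, SE of the log odds ratio = √(12/(120 × 0.98)) = 0.32. The 95% limits lie a factor of exp(1.96 × 0.32) ≈ 1.9 either side of the estimate.

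**The case against.** The strongest reply is that received is loose shorthand for the baseline factor. SAP 25d and section 26 both attach the minimisation label, and Table 1 puts receipt of alteplase under Admission with the minimisation dagger. That reading is plausible but not safe. The narrower term appears in all three analysis passages, Table 1 has no candidate row, and no time limit is given.

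A reader might infer that the covariate is simply a post-randomisation variable. The documents do not support that. The patch-first provision covers only patients without capacity or a relative present, and the protocol's table of completed trials records thrombolysis before GTN in the hospital-based ENOS trial. Receipt is mixed, in unknown proportion.

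A reader might also infer that the GTN estimate is biased, or even reversed in sign. Bias needs GTN to change receipt after randomisation. The protocol says only that it may, as one of several mechanisms, on non-significant trends. The reversal in step 3 needs a large assumed effect on receipt and an assumed direction for unmeasured prognosis.

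Two safeguards stand. SAP 25g plans an unadjusted ordinal analysis of mRS, which does not use this covariate, although it covers neither the subgroup nor other outcomes, and the other sensitivity model keeps the adjusted set. The comparisons are also labelled exploratory, the protocol disclaims confirmatory testing, and progression rests on recruitment, compliance and follow-up.

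**Conclusion.** The mismatch between the minimisation factor and the analysis variable is certain from the text. That the literal covariate can bias the adjusted exploratory comparisons and the reperfusion subgroup follows from it; that it will do so is not established.

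The size is unknown. It is nil if GTN does not change receipt or if all receipt precedes randomisation. It is about 3% to 7% on the common odds ratio, away from benefit, in the assumed scenarios of step 2 where GTN does change receipt. It is larger, and can run either way, only under the stronger assumptions of step 3. A shift of 3% to 7% is small against an interval a factor of 1.9 wide on each side. The feasibility endpoint and the unadjusted mRS analysis do not depend on it.

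This should be corrected because it is cheap and restores the SAP's stated intent. It does not threaten the trial's main conclusion.

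**What to change.** - In SAP 25d, section 26 and the Table 3 footnote, replace received reperfusion therapy with: candidate for or received reperfusion therapy, as recorded at randomisation.
- Add that factor to Table 1 as a row carrying the minimisation dagger, and remove the dagger from receipt of alteplase.
- Compare actual thrombolysis and thrombectomy between arms only as outcomes, for example as two rows under hospital interventions in Table 6. At present their only table shell is Table 1, which has no column for a between-arm estimate.

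Moving the Day 0 and 1 treatment rows out of Table 1 is a matter of layout and is optional.

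The cost is SAP wording and a few table rows. The value was needed to run the minimisation, so no new data collection should be required. If the sponsor meant the baseline factor all along, no analysis changes. The edit should be made before allocation is released, since a later change of covariate would be post hoc.

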### **25e Assumption checking:**

The assumption of proportionality will be tested using the likelihood test.

### **25g Sensitivity analyses:**

In addition to assessment of raw data, the primary clinical outcome (mRS) will be analysed using additional statistical approaches in sensitivity analyses using:

- Comparison using unadjusted ordinal logistic regression
- Comparison using adjusted multiple linear regression

### **26 Subgroup analyses:**

The primary clinical outcome will be analysed in subgroups consisting of the minimisation factors:

- Age (years):  $\leq 70$ ,  $> 70$
- Stroke severity, NIHSS (/42):  $\leq 10$ ,  $> 10$
- Time after stroke (minutes):  $\leq 220$ ,  $> 220$
- Systolic blood pressure (mmHg):  $\leq 160$ ,  $> 160$
- Received reperfusion therapy: yes, no

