## SYNOPSIS

Title	Efficacy of Nitric Oxide in Stroke-2 (ENOS-2)
Acronym	ENOS-2
Short title	Efficacy of Nitric Oxide in Stroke-2 (ENOS-2)
Chief Investigator	[name] Deputy Chief Investigator: [name]
Objectives	To assess the feasibility of recruitment and safety of transdermal glyceryl trinitrate (GTN) versus sham applied between 3 and 5 hours of stroke to inform a definitive trial.
Trial Configuration	Prospective randomised single-blinded masked-endpoint phase IIb trial.
Setting	Adults with hyperacute stroke presenting at emergency departments and hyperacute stroke units in England.
Sample size estimate	This is a feasibility study so there is no formal sample size calculation. (But recruitment of 100 participants would allow an adjusted common odds ratio, acOR 0.51 to be detected, assuming mRS distribution as in  ; alpha 0.05, power 0.80.)  It is likely that a large definitive trial would be feasible if at least 70 participants were recruited into this study. Lower recruitment would not preclude progression if there was some evidence that the barriers to recruitment identified could be overcome.
Number of participants	
 
• 100 with ischaemic stroke (50 randomised to GTN, 50 randomised to sham)
 
• 20 with intracerebral haemorrhage (for safety) (10 randomised to GTN, 10 randomised to sham)
 

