- GTN is safe in patients with severe carotid stenosis.

Further, the effect of GTN on functional outcome appears to be time-dependent when administered after stroke:

[figure not shown]
- <2.0 hours: No effect; indeed, GTN may cause harm in ICH in this ultra-acute period (interpretation from RIGHT-2 )
- 2.5 to 5.5 hours: May improve functional outcome (interpretation from ENOS-early  and meta-analysis, Figures 1 , 2).
- >6 hours: No effect (interpretation from GTN 1/2/3 and ENOS and an individual patient data meta-analysis ).

(The positive effect of GTN on functional outcome in the phase II RIGHT trial is ignored here because it was small.)

**Figure 1. Meta-analysis of GTN versus no GTN on end of trial functional outcome in patients treated within 6 hours of stroke onset (from )**

**Figure 2. Meta-analysis of GTN versus no GTN on end of trial death in patients treated within 6 hours of stroke onset (from )**

In summary, GTN has been associated with beneficial effects on function and other clinical outcomes in hospitalised patients treated up to 6 hours after ictus. However, benefit was not seen in patients treated prior to hospital admission and there was weak evidence that ultra-acute treatment within 2 hours was associated with harm. As a result, ENOS-2 will assess, in a novel design, the feasibility of recruiting patients between 3 and 5 hours after ictus; if feasible, a larger safety and efficacy trial will be performed in this group of patients.

ENOS-2 will assess the feasibility, safety, and efficacy of hospital-delivered GTN when administered hyper-acutely after stroke. Five of the six GTN trials had a lower limit for systolic blood pressure of  $\geq 100$  mmHg,  $>120$  mmHg or  $\geq 140$  mmHg, the first study had no lower limit. Since several potential mechanisms by which GTN might work are BP-independent, ENOS-2 will follow the RIGHT-2 protocol and include patients with high-normal BP as well as high BP, with a lower limit set to  $\geq 120$  mmHg. This has the advantage that the results will apply to a wider population of stroke patients and include more patients with severe stroke (some of whom have SBP  $<140$  mmHg).

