### **Stopping rules and discontinuation**

The DMC review unblind data twice yearly in respect of safety and efficacy and consider the study in the context of other trials of altering BP in stroke. Since the main aim of the study is to assess feasibility, the trial will not be discontinued unless the safety of participants is likely to be compromised. The DMC also monitor SAEs and neurological deterioration, and outcome in IS and ICH separately.

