### **9 Sample size/power considerations**

ENOS-2 is a feasibility study hence there is no formal sample size calculation. However, recruitment of 100 participants would allow an adjusted common odds ratio, acOR 0.51 to be detected, assuming mRS distribution as in; alpha 0.05, power 0.80. The number of targeted participants will be 100 with ischaemic stroke (50 randomised to GTN, 50 randomised to sham) and 20 with intracerebral haemorrhage for safety (10 randomised to GTN, 10 randomised to sham).

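### Stroke type, the only stratification factor, is missing from the SAP's covariates and subgroups, and no planned table shows results by arm within ICH

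*SAP*

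**What the plan says.** Both documents make stroke type the single stratification factor. The SAP (section 11) describes "computerised stratification by stroke type (IS or not known; ICH)", and the protocol (Randomisation and Blinding) says the same. Age, severity, time, systolic pressure and reperfusion are handled by minimisation. SAP section 31 lists the stratification among its safeguards against bias.

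The ICH cohort has a stated purpose. SAP section 9 plans "20 with intracerebral haemorrhage for safety (10 randomised to GTN, 10 randomised to sham)", beside 100 participants with ischaemic stroke. Under Stopping rules and discontinuation, the protocol has the DMC monitor SAEs, neurological deterioration and "outcome in IS and ICH separately"; SAP 12a repeats this.

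The analysis sections do not carry stroke type forward. SAP 25d says "Analyses will be adjusted for minimisation covariates including age, stroke severity (NIHSS), time after stroke", then adds systolic pressure and received reperfusion therapy. The Table 3 footnote gives the same five as a closed list. Section 26 says "The primary clinical outcome will be analysed in subgroups consisting of the minimisation factors" and names those five. Section 28 only promises a table of SAEs.

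**The concern.** A factor important enough to stratify on would normally be in the model and in the subgroup list. Here it is in neither. The larger matter is reporting. A cohort recruited for safety should lead to a safety result, and no planned output gives deaths, SAEs, deterioration or mRS by arm among the ICH patients. The trial's objective is to inform a definitive trial, whose designers will want to know what happened in each stroke type. If the split is first made after the randomisation codes are released, it becomes a post hoc table.

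**Working it through.** **Step 1: where stroke type appears in the SAP.**

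| Place | Use of stroke type |
|---|---|
| 25d, covariates | Not listed, although the word used for the list is not exhaustive |
| Table 3 footnote, covariates | Not listed; closed list |
| Section 26, subgroups | Not listed |
| Table 1, baseline | Scan result by arm |
| Table 2, feasibility | Recruitment counts for IS and ICH |
| Table 3, day 90 | Columns by arm only |
| Table 4, day 2 | Columns by arm only; rows for symptomatic ICH, ICH expansion and type of recurrent stroke, over all randomised patients |
| Table 6, discharge | Final diagnosis by arm |
| Tables 8 and 9, SAEs | Columns by arm only |

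Stroke type is therefore counted, but no outcome or SAE is cross-tabulated against it. The reperfusion subgroup is no substitute, because patients without reperfusion include untreated IS as well as ICH.

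**Step 2: the plan's own figure.** The documents state no power, precision or event rate for the ICH cohort, so there is nothing to reproduce on this point. The one sample-size figure (100 participants, common odds ratio 0.51) is a separate question and is not used here.

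**Step 3: dilution.** Inputs from SAP section 9 are 50 IS and 10 ICH per arm.

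Pooled risk difference = (50 × difference in IS + 10 × difference in ICH) / 60.

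With no effect in IS, the pooled table shows 10/60 = one sixth of the ICH difference. Take an assumed 20% event risk on sham in both types and no effect in IS:

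| GTN risk in ICH (assumed) | Difference in ICH | Pooled difference | Power, ICH 10 v 10 | Power, pooled 60 v 60 |
|---|---|---|---|---|
| 40% | 20 points | 3.3 points | 6% | 4% |
| 50% | 30 points | 5.0 points | 13% | 7% |
| 60% | 40 points | 6.7 points | 25% | 9% |

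Power is for the two-sided Fisher exact test at 0.05. For the middle row, the pooled GTN risk is (50 × 0.20 + 10 × 0.50)/60 = 15/60 = 25%, against 20% on sham. If GTN also lowered the IS risk to 14%, the pooled GTN risk would be (7 + 5)/60 = 20%. A 30-point excess in ICH would then cancel exactly.

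**Step 4: what a separate ICH report can show.**

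- Zero events in 10: two-sided exact upper limit = 1 − 0.025^(1/10) = 0.308, or 31%.
- With no events in one arm, the smallest split that reaches p ≤ 0.05 is 5/10 v 0/10 (Fisher p = 0.033).
- mRS, proportional odds, 20 patients, seven equally likely levels (assumed, so the sum of p³ is 1/49): SE of log OR = √[12/(20 × 48/49)] = 0.78. The 95% interval is the estimate multiplied or divided by about 4.6. Power of 80% needs an odds ratio of about 9.0 (or 0.11).

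The split shows any ICH difference at full size but cannot test it.

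**The case against.** The strongest counter-argument is that no trial decision depends on this. The primary endpoint is feasibility, progression rests on recruitment, compliance and follow-up, and treatment comparisons are exploratory. A 10 v 10 comparison will settle nothing. All of that stands. It limits the severity, and it means the ICH results should be descriptive. It does not explain why a cohort enrolled for safety has no safety output.

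A reader might infer several stronger claims that the documents do not support.

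- *That harm in ICH would go unseen.* It would not. The DMC reviews unblinded data twice yearly by stroke type, and Table 4 has two rows for ICH events. Neither replaces a final report: the protocol says the DMC will not pass specific unmasked results to the steering committee or chief investigator. The Table 4 rows cover all randomised patients, and the only scan in the schedule is at baseline, so expansion is not measured systematically.
- *That the protocol expects harm in ICH in this trial.* The background does say "GTN may cause harm in ICH in this ultra-acute period", but that line concerns treatment under 2 hours. ENOS-2 treats at 3 to 5 hours; the protocol lists 2.5 to 5.5 hours as possibly beneficial and calls GTN safe after 2.5 hours.
- *That pooling would produce an apparent benefit of known size.* Any such figure needs an assumed odds ratio in ICH, and the documents give none.
- *That omitting the stratifier invalidates the intervals.* Conservative intervals in an exploratory analysis are not a validity failure. In ordinal and logistic models, adding a prognostic covariate also changes the odds ratio being estimated. No loss of precision has been quantified here. The case for adjusting is consistency with the design.

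One practical objection also stands: with about 20 ICH patients, a binary model that includes the stratum may not be estimable when a stratum has no events.

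**Conclusion.** The gap is real and should be fixed, but it does not threaten the feasibility conclusion. As written, the SAP neither adjusts for its only stratification factor nor reports any outcome or SAE by arm within IS and within ICH. The six-fold dilution follows from the planned numbers alone (20 of 120, equal allocation) and would change if recruitment by type differed. The event risks and the mRS distribution in the worked examples are assumptions. A separate ICH report would have very low precision, so its value is transparency and planning for the definitive trial, not inference.

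**What to change.** Before the randomisation codes are released, amend the SAP as follows.

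1. **Covariates.** Add the randomisation stratum (IS or not known; ICH) to 25d and the Table 3 footnote wherever it is estimable. State that it is dropped for binary outcomes with no events in a stratum.
2. **Subgroups.** Add stroke type to section 26, descriptive only for ICH.
3. **Tables 3, 4, 8 and 9.** Show mRS, deaths, SAEs, neurological deterioration and hypotension by arm within IS and within ICH. Give exact 95% intervals for event counts and no tests in ICH.
4. **Definition.** Use the randomisation stratum in the adjusted models and the final diagnosis (already in Table 6) for the descriptive split. The two can differ, because patients of unknown type are randomised with IS and the scan may follow treatment. Say where transient ischaemic attack, unknown type and non-stroke diagnoses are shown, so that the counts add up.
5. **Precision.** State that the ICH results are descriptive, with the 0/10 upper limit of 31% as the illustration.

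The cost is SAP wording and extra table columns or panels, with no new data collection. The drawback is that the ICH estimates will be very imprecise and must be labelled so.
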